3.1 Primary Objectives

- Aim 1: To evaluate the effects of the ATTOC intervention on provider adherence to the USPHS clinical practice guidelines for treating TUD. Hypothesis: At the end of the intervention and at a 3-month follow-up, rates of adherence to guidelines for treating TUD will be greater among clinic personnel that receive the ATTOC intervention vs. clinic personnel in usual care.
- Aim 2: To assess the effects of the ATTOC intervention on rates of client smoking. Hypothesis: At the end of the intervention and at a 3-month follow-up, rates of client smoking cessation will be significantly greater in clinics that receive the ATTOC intervention than among clients treated with usual care.
- Aim 3: To evaluate the effects of the ATTOC intervention on client mental health functioning and quality of life (QOL). Hypothesis: Using non-inferiority testing, at the end of the intervention and at a 3-month follow-up, there will be no significant degradation in mental health functioning or QOL among clients who receive care at clinics that received the ATTOC intervention than among clients treated with usual care.

3.2 Secondary and Exploratory Objectives

[figure not shown]
- Secondary Aim: To assess the cost-effectiveness of the ATTOC intervention. Hypothesis: ATTOC will have a favorable incremental cost-effectiveness ratio measured as dollars/quitter and dollars/life-year saved.
- Exploratory Aim 1: We will assess changes in cultural and systemic barriers to treatment as mediators of the effects of the ATTOC model on provider adherence to guidelines for treating TUD and client smoking.
- Exploratory Aim 2: To inform model dissemination, we will identify components of the ATTOC intervention that predict greater change in provider adherence to guidelines for treating TUD and client smoking.

4 Investigational Plan

4.1 General Design

This cluster-randomized trial will be conducted with 14 Philadelphia CMHCs, 7 randomized to ATTOC and 7 to usual care (UC). Following randomization, study staff will visit sites to recruit clinic personnel and clients over a 4 to 6 week period. Those eligible will complete informed consent and HIPAA forms and a baseline assessment to establish pre-intervention levels on all measures (baseline). After 4-6 weeks, the ATTOC intervention will be implemented over 9 months, from Week 1 to Week 36 (with UC at the control sites). Two mid-intervention assessments (Weeks 12 and 24) will allow for performance feedback (see Outcomes Data) and mediational analyses. Week 36 (end-of-treatment; EOT) and 52 (3-months post-EOT) assessments will allow for evaluation of changes on outcomes between groups over time. All measures will be conducted at the respective CMHC

(or over the phone if necessary) and 7-day point prevalence smoking cessation will be verified using a breath carbon monoxide (CO) monitor (abstinence = < 8ppm; [93]). Figure 1 illustrates the study design.

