4.2 Randomization to Interventional Group

Although randomization and inclusion criteria will increase comparability between arms, sites will be matched by: 1) size (i.e., moderate [15-30 personnel; 110-249 clients] vs. large [>30 personnel; >249 clients]) 2) organizational motivation (e.g., < 30 vs. ≥ 30 on sum of all 12 items from the Organizational Readiness for Implementing Change [ORIC] measure [92]). We will try to enroll >2 sites (1/arm) that do not respond to initial invitations to enroll to include CMHCs with low readiness to implement change. Using the ORIC and outreach to sites with low motivation, we hope to reduce the potential of over-volunteering that can limit generalizability. If a CMHC has multiple locations, all locations will be randomized to the same arm but they will be considered 1 of the 14 randomized sites. Once eligible and interested sites are identified, using the small-sample equivalent to matching on stratification data, they are randomly assigned to UC or ATTOC. Computerized randomization within our Data Management System (DMS) will be provided by [name]. Once randomized, participants (personnel and clients) will be recruited for the trial.

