4.3 Rationale for Study Design

An alternative design would involve randomization of clients and providers within the agencies. Although that could avert potential confounds attributable to differences between agencies, we considered the risk of contamination – and, thus, a threat to internal validity – from such a design to be too probable. While an agency-level randomization may be subject to confounding as well, we will match the agencies on key variables before randomization to increase control over potential treatment confounds and we will use appropriate analytic models to account for this potential confounding (see Data Analysis). We also considered either: 1) not including a control arm; or 2) providing a more potent control arm, but considered the present design one that would allow for more convincing conclusions about the effects of ATTOC vs. current practice. Thus, we viewed the proposed design to be the ideal balance between internal and external validity.

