Once sites are randomized, we will use a 4 to 6 week window for subject recruitment. This will allow study staff to recruit in-person for multiple days and across several weeks to ensure that we access all site personnel and a representative sample of clients. We have experience recruiting in clinic settings [59, 71] and have 2 ongoing studies that follow such procedures (R01 CA165001; R01 DA033681). If the 4-6 week period is not sufficient time to recruit a participant sample, the Principal Investigator reserves the right to lengthen the recruitment window by 4-6 weeks. The Principal Investigator may also need to under-enroll clinic personnel or client participant groups at certain sites due to organizational constraints. This under-enrollment will be supplemented at larger clinics by over-enrolling participants at other sites. In order to prevent possible retribution against clinic

personnel on the part of clinic leadership, we will not disclose the enrollment decisions of clinic personnel, and we will offer smoking cessation resources to the clinic.

To recruit personnel, we will use staff meetings, electronic and written communication, and hold study-specific meetings. To recruit clients, as done now (R01 CA126969), but modified as needed upon advice from the Community Advisory Council, our Research Assistants (RAs) will assess every scheduled client for interest and eligibility using clinic schedules to approach clients prior to or after appointments. We post program flyers and brochures in clinics as well. Participants who are eligible and interested in the study will be scheduled for an intake session. To assess external validity, eligible personnel and clients who refuse entry will be compared to those who enroll based on available data (e.g., smoking status, years employed, nature of SMI).

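### Staff and clients are recruited after their clinic is randomised, with no stated concealment of arm and no baseline covariates prespecified for the primary models, so who enrols can differ by arm

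*Combined protocol and SAP*

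**What the plan says.** The order of events is given three times.

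- Section 4.1: "Following randomization, study staff will visit sites to recruit clinic personnel and clients over a 4 to 6 week period".
- Section 4.2: "Once randomized, participants (personnel and clients) will be recruited for the trial".
- Section 5.5: "Once sites are randomized, we will use a 4 to 6 week window for subject recruitment".

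Section 5.5 also leaves enrolment open to change after allocation: "the Principal Investigator reserves the right to lengthen the recruitment window by 4-6 weeks". Where a site under-enrols, "This under-enrollment will be supplemented at larger clinics by over-enrolling participants at other sites". Neither provision has to be exercised blind to arm or kept within arm.

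The plan contains several safeguards.

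- Clinics are matched on size and organisational readiness (4.2). On confounding between agencies, section 4.3 says "we will use appropriate analytic models to account for this potential confounding".
- University staff do the recruiting (section 1), and research assistants assess every scheduled client (5.5).
- All supervisory and clinical staff are eligible (section 5), with 90–100% uptake expected (6.1).
- For external validity, "eligible personnel and clients who refuse entry will be compared to those who enroll based on available data" (5.5); this is not stated to be by arm.
- Sample characteristics are checked by arm and site (7.2).
- Baseline data are meant to allow control of differences across usual-care sites (6.1.1).

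On covariates, section 4.7 lists client psychiatric history and a COVID-19 questionnaire, and Table 4 lists demographics, smoking history and FTND. Section 7.2 makes entry optional for variables related to arm or follow-up completion at p<.10. Section 7.2.1 leaves covariates optional for Aim 1 and mentions them without naming any for Aim 2.

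**The concern.** Randomising clinics protects the comparison of clinics. It does not protect the comparison of people who decide whether to join once the arm is known. If clients keener to quit join more readily in one arm, Aim 2 quit rates can differ for reasons unrelated to ATTOC. Aim 3 is exposed in the same way if clients' mental health at entry differs by arm.

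The documents show how knowledge of arm could reach enrolment. ATTOC leaders know their allocation before Week 1 and are advised on preparing staff (6.1.2), and site directors distribute the staff recruitment material (6.1). The only blinding statement (7.2) concerns whether clinicians learn which clients enrolled, not whether anyone knows the arm.

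The remaining protection is adjustment, and the plan does not fix it. An optional screen can miss an imbalance that matters and leaves the final model open until the data have been seen.

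**Working it through.** **1. The plan's own Aim 2 figures.** Inputs from section 7.1: 700 clients in 14 sites (350 per arm, 50 per site), usual-care quit rate 2% (stated as below 2%), α .05, 80% power. Sidedness is not stated for Aim 2; two-sided is assumed. Effective n per arm = 350/(1 + 49 × ICC). Solving the pooled two-proportion formula for the detectable difference gives:

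| ICC | Effective n per arm | Recomputed (points) | Stated (points) |
|---|---|---|---|
| 0 | 350 | 4.19 | 4 |
| .05 | 101.4 | 9.97 | 10 |
| .10 | 59.3 | 14.90 | 15 |
| .15 | 41.9 | 19.39 | 19 |

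The figures reproduce, so sample size is not in dispute. The issue is bias.

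**2. How well the p<.10 screen detects a client imbalance.** Assumptions: a true difference of 0.2 SD between arms on a client baseline variable, and an ICC for that variable in the range section 7.1 uses for outcomes (the documents give none for baseline variables). SE of the standardised difference = √(2/effective n). Power ≈ Φ(0.2/SE − 1.645).

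| ICC | SE | 0.2/SE | Chance of being flagged |
|---|---|---|---|
| 0 | 0.0756 | 2.65 | 84% |
| .05 | 0.1404 | 1.42 | 41% |
| .10 | 0.1836 | 1.09 | 29% |

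With only 14 clinics, the normal approximation slightly flatters the screen.

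Section 7.2 specifies chi-square or regression for this check and does not say that it allows for clustering. If it does not, then at ICC .05 a variable with no systematic arm difference is flagged with probability 2 × [1 − Φ(1.645/√3.45)] = 2 × [1 − Φ(0.886)] ≈ 38%. The screen then picks up noise.

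**3. What 0.2 SD means.** Section 7.1 gives a BASIS-R SD of 0.8, so 0.2 SD is 0.16 units. The plan's detectable non-inferiority difference is 0.19 at ICC=0 and 0.50 at ICC=.15, so 0.16 is 84% or 32% of it. This is a scale for judging an imbalance, not an estimate of bias.

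**4. Size of any Aim 2 bias.** With no true effect, spurious difference = (arm gap in the share of motivated clients) × (gap in quit probability between motivated and other clients). The documents give neither term for this population, so no figure follows.

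**5. Room for selection among clients.** About 50 clients per site are enrolled (5.2) from a load of 200–300 (5.5), but only smokers are eligible. Assuming the 37–69% smoking prevalence by diagnosis in section 2.1, a clinic has 200 × .37 = 74 to 300 × .69 = 207 smokers, and 50 is 68% to 24% of them. The fraction is rough, because the five-cigarettes-a-day criterion is narrower still.

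**The case against.** The best defence is that the plan limits recruiter discretion. University staff recruit, every scheduled client is assessed, and staff recruitment is close to a census. This stands in part. It makes the staff comparison much less exposed and restricts whom recruiters choose to approach. It does not stop clients, or the leaders who shape a clinic's message, from responding differently once the arm is known. Section 4.3 addresses differences between agencies, which is a separate problem.

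Several stronger readings are tempting but not supported.

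- A reader might infer that no baseline covariates are named. Section 4.7 and Table 4 list them; what is missing is a fixed set in the models.
- A reader might size the bias from the Connecticut data in section 2.2, taking 13% and 7% as quit rates for more and less motivated clients. Any mix of those rates is at least 7%, which cannot coexist with a usual-care rate below 2%, and both come from agencies implementing ATTOC.
- A reader might take 50 of 200–300 as the enrolled fraction. That denominator includes non-smokers.
- A reader might infer that baselines follow training at COMHAR and Merakey. Section 4.5 places personnel training before recruitment closes, but does not say that staff baselines are still open then, and it does not state either clinic's arm. Overlap is possible, not established. A late baseline would not bias an unadjusted comparison of week 36 and 52 levels; it would be a poorer covariate.

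**Conclusion.** The point holds. Followed as written, the plan allows enrolment, chiefly of clients, to differ by arm, and its safeguards reduce this risk without removing it. The analysis does not make up the gap, because covariates are optional and their selection rule would miss a 0.2 SD client imbalance more often than not at ICC .05 (59%) or .10 (71%). These percentages rest on the assumed imbalance and ICCs.

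The documents do not show that differential enrolment occurs, which arm it would favour, or how large it would be. It would be wrong to conclude that ATTOC's effect is inflated. The finding on concealment is limited to the visible text, since the consent pages could not be checked.

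A separate, minor point: section 4.5 needs reconciling with section 4.1, which describes "a baseline assessment to establish pre-intervention levels on all measures (baseline", and with Table 4 footnote 1, which puts baseline before Week 1.

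**What to change.** 1. **Any wave not yet recruited.** Collect matching data at clinic screening as now, but run or disclose the randomisation only after that wave's recruitment and baselines are complete. Decide window extensions and enrolment shifts before disclosure. The cost is a protocol amendment, shorter notice for ATTOC preparation calls and trainer travel, and a slightly longer gap from baseline to Week 1. The documents do not show whether any wave remains; if none does, only the steps below apply.

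2. **All clinics.** Replace the p<.10 arm-imbalance screen with a fixed set: baseline S-KAP for Aim 1; baseline BASIS-R and SF-12 for their Aim 3 outcomes; and for Aim 2 a short list such as FTND and smoking rate from the smoking history. Keep the Aim 2 list small because quitters will be few. At the plan's detectable differences there would be 350 × 2% + 350 × 6% = 28 at ICC=0, or 350 × 2% + 350 × 12% = 49 at ICC=.05; these are not predictions. S-KAS attitudes are optional, since they concern quitting in relation to the clinic setting (4.7). Keep variables related to follow-up completion for the missing-data analysis. All these measures are already collected at baseline, so the cost is a short analysis addendum. Adjustment will not remove differences in unmeasured motivation.

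3. **Reporting.** Present the refuser–enrollee comparison by arm.

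4. **Baseline timing.** Reconcile section 4.5 with section 4.1 and Table 4 footnote 1. Flag any baseline that follows training and repeat the analyses without those participants. Treat this as a sensitivity analysis only, because it selects on an event after randomisation.

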4.2 Randomization to Interventional Group

Although randomization and inclusion criteria will increase comparability between arms, sites will be matched by: 1) size (i.e., moderate [15-30 personnel; 110-249 clients] vs. large [>30 personnel; >249 clients]) 2) organizational motivation (e.g., < 30 vs. ≥ 30 on sum of all 12 items from the Organizational Readiness for Implementing Change [ORIC] measure [92]). We will try to enroll >2 sites (1/arm) that do not respond to initial invitations to enroll to include CMHCs with low readiness to implement change. Using the ORIC and outreach to sites with low motivation, we hope to reduce the potential of over-volunteering that can limit generalizability. If a CMHC has multiple locations, all locations will be randomized to the same arm but they will be considered 1 of the 14 randomized sites. Once eligible and interested sites are identified, using the small-sample equivalent to matching on stratification data, they are randomly assigned to UC or ATTOC. Computerized randomization within our Data Management System (DMS) will be provided by [name]. Once randomized, participants (personnel and clients) will be recruited for the trial.

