5.2 Total Number of Subjects and Sites

A total of 14 CHMC sites will be recruited for the trial. At each site, 12-30 staff and about 50 clients will be recruited (Total N: Staff = ~280; Clients = ~700). Procedures will be standardized across sites.

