5.3 Inclusion Criteria

Participating CMHCs must meet the following criteria for enrollment:

1. Must use an electronic health record (EHR)
2. Must report client prescription data to Community Behavioral Health (CBH)
3. Must have at least 12 personnel who have clinical interactions with clients

Clinic personnel participants must meet the following criteria for enrollment:

1. Must be 18 years of age or older
2. Must perform clinical care or supervisory duties
3. Must demonstrate the ability to communicate in English and provide written or verbal informed consent

Clinic client participants must meet the following criteria for enrollment:

1. Must be 18 years of age or older
2. Must report daily average smoking of 5 cigarettes/day for the past 6 months
3. Must have a documented DSM Axis I or II disorder
4. Must demonstrate the ability to communicate in English and provide written or verbal informed consent

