5.5 Subject Recruitment

The study will be implemented within Philadelphia's CBH provider network, which encompasses the >300 CMHCs that provide care to the city's >470,000 Medicaid recipients. The CBH Chief Medical Officer, and the Executive Directors of the Philadelphia Coalition, the Philadelphia Alliance, and MHASP, which represent >70 CMHCs and oversee educational initiatives within the agencies, will assist with recruiting agencies. A notice describing the opportunity to enroll in the study will be sent from [name], [name], [name], and [name] to CMHC directors, with instructions on how to ascertain information or to enroll (monthly meetings are also held by the Alliance, Coalition, and MHASP with CMHC CEOs and the research team has and will attend these meetings to publicize the study).

Clinic recruitment will include a brief survey including the ORIC measure to collect stratification data to reduce the risk for selection bias and increase the probability of generalizability. [name], [name], [name], and [name] will attempt to enroll >2 sites (1/arm) that do not respond to invitations. To assess sample generalizability, we will compare enrolled site characteristics (e.g., size, composition) to data available for all CMHCs at CBH. Each agency maintains a staff of 12-40 and a client load of >200-300, indicating that recruiting 14 sites will meet recruitment goals. While we opted for this prospective recruitment method to facilitate accurate stratification (vs. identifying all sites up-front), our pilot work recruited >167 mental healthcare clinicians for a training in treating TUD in one year and an ongoing trial with PENN and CBH to promote evidence-based treatment for youth mental illness used this approach to recruit 23 clinics [91].

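### The size bands used to match clinics are neither exhaustive nor mutually consistent for the clinics the protocol admits and expects, and no placement rule is given

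*Combined protocol and SAP*

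**What the plan says.** Section 4.2 matches clinics on two factors. The first is size, in two bands: "moderate [15-30 personnel; 110-249 clients] vs. large [>30 personnel; >249 clients". The second is "organizational motivation (e.g., < 30 vs. ≥ 30 on sum of all 12 items" of the readiness questionnaire (ORIC). On allocation the section says: "using the small-sample equivalent to matching on stratification data, they are randomly assigned to UC or ATTOC". It gives no algorithm beyond computerised randomisation in the data management system. It does not say whether the two counts in a bracket must both hold, or what happens to a clinic outside the brackets.

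Four other places describe the clinics to which the bands apply:

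- Section 5.3 sets the clinic floor: "Must have at least 12 personnel who have clinical interactions with clients". It sets no client minimum.
- Section 5.5 describes the pool: "Each agency maintains a staff of 12-40 and a client load of >200-300".
- Section 5.2 plans recruitment from small clinics upward: "At each site, 12-30 staff and about 50 clients will be recruited".
- Section 4.1 fixes the number of clusters: "14 Philadelphia CMHCs, 7 randomized to ATTOC and 7 to usual care (UC".

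Section 4.3 names matching before randomisation, together with the analytic models, as the control on confounding between agencies. Section 4.6 brings sites in over four waves of 3, 4, 4 and 3. Section 7.2 allows as covariates those variables related to arm or to completion of follow-up at p < .10. It does not name the matching factors.

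**The concern.** A stratification rule must give every eligible unit exactly one label. This one leaves some eligible clinics with no label or with conflicting ones, and nothing elsewhere in the document resolves them.

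With 7 clinics per arm, matching is a named safeguard and there is little room for slack. Two size levels by two readiness levels make four cells, or 14 / 4 = 3.5 clinics per cell on average, so one or two ambiguous clinics can affect the balance that matching is meant to secure. Sites also enter over time, so a clinic may have to be labelled after earlier ones are already allocated. If the label is not fixed by a written rule, the record will not show how it was reached, and an analysis by stratum cannot be reproduced.

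**Working it through.** The plan states no share of unclassifiable clinics, so there is no figure to reproduce. The inputs are the bands (section 4.2), the floor of 12 (section 5.3), the ranges of 12-40 staff and 200-300 clients (section 5.5) and the 14 clinics (section 4.1). The joint distribution of staff and clients is not given; everything from step 3 on assumes one.

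**1. Each count alone.** Staff of 12, 13 and 14 are eligible and expected but below 15. That is 3 of the 29 integers from 12 to 40, or 10.3%. If each value is equally likely, 14 × 0.103 = 1.4 clinics. Client count alone leaves no gap within 200-300, since the bands run from 110 upward.

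**2. The two counts together.** Both cuts (30/31 staff, 249/250 clients) fall inside the expected ranges.

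| Staff | Clients | Both counts required | Either count suffices |
|---|---|---|---|
| 15-30 | 200-249 | moderate | moderate |
| 31-40 | 250-300 | large | large |
| 15-30 (e.g. 20) | 250-300 (e.g. 270) | none | both |
| 31-40 (e.g. 35) | 200-249 (e.g. 220) | none | both |
| 12-14 | 200-249 | none | moderate |
| 12-14 | 250-300 | none | large |

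A discordant clinic has no unique stratum on either reading. The 12-14 gap closes only on the second.

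**3. Illustrative share, uniform and independent sizes, both counts required.** The grid has 29 × 101 = 2,929 combinations.

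- Classified: 16 × 50 + 10 × 51 = 800 + 510 = 1,310, or 44.7%.
- 12-14 staff: 3 × 101 = 303, or 10.3%.
- 15-30 staff with more than 249 clients: 16 × 51 = 816, or 27.9%.
- More than 30 staff with 249 clients or fewer: 10 × 50 = 500, or 17.1%.
- No stratum: 303 + 816 + 500 = 1,619, or 55.3%; 14 × 0.553 = 7.7 clinics.

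**4. Uniform sizes rising in step.** The lowest 3/29 = 10.3% have 12-14 staff. Staff passes 30 at the 19/29 = 65.5% point, and clients pass 249 at the 50/101 = 49.5% point. Discordant: 65.5 − 49.5 = 16.0%. No stratum: 10.3 + 16.0, which is 26.4% before rounding; 14 × 0.264 = 3.7 clinics. Intermediate dependence (Gaussian copula) gives 43.5% at correlation 0.5, 37.8% at 0.7 and 29.9% at 0.9.

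**5. If either count suffices.** The discordant clinics then fit both bands: (816 + 500) / 2,929 = 44.9% if independent, 16.0% in step.

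**6. Other shapes on the same ranges.** Replacing the uniform margins by Beta(2,4), Beta(4,4) and Beta(4,2) in all pairings, independent or nearly in step, moves the no-stratum share from 0.7% (staff Beta(4,4), clients Beta(2,4), in step) to 85.3% (staff Beta(2,4), clients Beta(4,2), in step).

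**The case against.** The strongest reply is that the brackets may only describe typical moderate and large clinics, and that the unspecified matching could use the raw counts collected at screening. The bands would then never be applied as a classifier. The document does not rule this out, but it does not say it either: section 4.2 presents the bands as the matching criterion.

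A reader might go further and infer three things that the documents do not support:

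- **That a quarter to a half of clinics fit no stratum by the protocol's own figures.** Section 5.5 gives ranges only, in an argument about recruitment feasibility. The 26-55% needs uniform sizes and the joint reading of each bracket, and both are assumptions.
- **That such clinics must be placed ad hoc.** The plan is silent on placement. That is under-specification; it does not show that judgement enters the allocation.
- **That the label decides the arm.** This needs a scheme in which the stratum fixes the next assignment. Section 4.2 says only that assignment is random.

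Matching is also not the only protection: section 4.2 puts randomisation and the inclusion criteria first, and sections 4.3 and 7.2 add modelling.

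Finally, the floor of 12 counts personnel with clinical contact, while the bands count personnel without that limit. A clinic with 12 client-facing staff may have 15 or more in all. This narrows the low-end gap but does not close it, because section 5.5 puts agency staff as low as 12.

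**Conclusion.** The point holds as a defect in a stated rule. The bands miss clinics with 12-14 personnel when both counts, or the staff count, must be met, and they give no unique label to clinics whose two counts disagree, whichever way the brackets are read. No other section supplies the missing rule.

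The number of clinics affected cannot be derived from the documents. The range of 26% to 55% (about 4 to 8 of 14) is an illustration under uniform sizes with both counts required. About 10% (1 to 2 of 14) follows from staff count alone with uniform sizes, and about 1% to 85% from other shapes. The conclusion needs none of these percentages. It is a minor point: it weakens a named safeguard and its documentation, and no power or error-rate figure depends on it.

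**What to change.** In section 4.2 and the randomisation specification, make the size rule exhaustive and mutually exclusive from 12 personnel upward, for clinics not yet randomised. Two options are equally open:

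- use one size measure, either staff (for example 12-30 versus more than 30) or clients; or
- keep both and state in advance which decides when they disagree, and where clinics with 12-14 personnel go.

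The documents do not favour one measure. Client count may be closer to the client outcomes of Aims 2 and 3, and staff count to Aim 1. State also whether the personnel count is all staff or only those with clinical contact.

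Sections 4.4 and 4.5 describe pandemic-era changes, so some clinics have presumably been randomised already. Do not relabel them: record the stratum actually used for each. In section 7.2, name the recorded matching factors (size and ORIC) as covariates in the outcome models, outside the p < .10 screen. A factor that matching has balanced will tend not to be picked up by a screen on its relation to arm.

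The cost is a line of text in section 4.2 and in the randomisation specification, a sentence in section 7.2, and one or two cluster-level degrees of freedom (with 14 clinics and two arms, from 14 − 2 = 12 to 10 if both factors enter). Earlier and later clinics may have been labelled under two rules; analysing by the recorded stratum handles that.
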